### 4.4 Selection of Patients

### 4.4.1 Inclusion Criteria

Each patient must meet all of the following inclusion criteria to be enrolled in the study:

Title: Absorption and Safety with Sustained Use of Relizorb™ Evaluation (Assure) Study in Patients With Cystic Fibrosis Receiving Enteral Feeding

1. Male or female patients 4 years of age or older

- Confirmed diagnosis of CF defined as two clinical features consistent with CF and have either:
  - a. Genotype with two identifiable mutations consistent with CF, determined using diagnostic devices that have been cleared by the US FDA (the FDA clearance requirement does not apply if the test was performed prior to 2005, the year the US FDA first started evaluating genetic tests for CF), or
  - b. Sweat chloride >60 mEq/L by quantitative pilocarpine iontophoresis
- Documented history of exocrine pancreatic insufficiency due to CF (e.g., historical fecal elastase test, genotype consistent with exocrine pancreatic insufficiency, etc.)
- Enteral formula user a minimum of four to five times per week, using PERT, consuming an unrestricted fat diet, and willing to use Peptamen 1.5 and Impact Peptide 1.5
- 5. Clinically stable with no significant changes in health status within 14 days of Day -14
- 6. Written informed consent obtained from patient, or, if the patient is a minor, from the patient's legal representative with assent from the minor when applicable.

### 4.4.2 Exclusion Criteria

Each patient who meets any of the following exclusion criteria will be excluded from the study:

- 1. Uncontrolled diabetes mellitus
- Signs and symptoms of liver cirrhosis or portal hypertension (e.g., splenomegaly, ascites, esophageal varices) or significant liver disease. Significant liver disease is defined as liver transaminases >3x upper limit of normal (ULN) or total bilirubin 1.5x ULN at baseline (or based upon the discretion of the Principal Investigator (PI)
- 3. Lung or liver transplant
- 4. Active cancer disease currently receiving cancer treatment
- Known small intestinal inflammatory diseases such as Crohn's or Celiac disease, or diarrheal illness unrelated to EPI (e.g., infectious gastroenteritis, sprue, lactose intolerance, inflammatory bowel disease)
- 6. History of fibrosing colonopathy or recurring distal intestinal obstructive syndrome (e.g. more than three occurrences per year)
- 7. CF respiratory exacerbations within 2 weeks prior to study entry

Title: Absorption and Safety with Sustained Use of Relizorb™ Evaluation (Assure) Study in Patients With Cystic Fibrosis Receiving Enteral Feeding

- 8. Oral glucocorticoid therapy or intravenous glucocorticoids within 2 weeks prior to baseline; patients who are receiving low dose alternate day corticosteroid therapy for lung disease may be enrolled in the study subject to consultation between the site PI and the Alcresta Chief Medical Officer
- 9. Major surgery or serious lung infection within 2 weeks prior to study entry
- 10. Acute life-threatening or uncontrolled medical illness
- 11. Known alcohol, drug or medication abuse
- 12. Any condition, in the judgment of the site PI, which would interfere with the intent of the study or make participation not in the best interest of the patient
- 13. For females of childbearing potential:
  - a. Positive pregnancy test at study entry
  - b. Lactating
  - c. Unwilling to use an effective medically acceptable form of contraception (e.g., prescription oral contraceptives, contraceptive injections, contraceptive patch, an intrauterine device, NuVaRing®, diaphragm with spermicide or abstinence) from baseline to the end of the study.
- 14. Treatment with investigational study agents (drug, biologic or device) other than Relizorb within 30 days of study entry
- 15. Adult subjects who lack the capacity to provide individual informed consent.

# 4.5 Patient Enrollment and Replacement Criteria

Approximately 30 to 35 patients will be enrolled in the study. Protocol compliant patients from Protocol 0000497 are eligible for this study, unless clinical changes have occurred in which the patient no longer meets the initial eligibility criteria. All eligible patients willing to continue in this study will be accepted. Every reasonable attempt should be made by study staff to assist eligible patients interested in participating in this study.

Any subject who withdraws from the study before Study Visit 3 on Day 30 will be replaced by an eligible patient.

Any subject who withdraws from the study before Study Visit 4 on Day 60 must be replaced by an eligible patient.

Any subject who withdraws from the study before Study Visit 5 on Day 90 may be replaced by an eligible patient unless the sum of completed subjects and currently enrolled and active subjects is greater than 30, in which case the subject will not be replaced unless the sum of completed subjects and currently enrolled and active

Title: Absorption and Safety with Sustained Use of Relizorb™ Evaluation (Assure) Study in Patients With Cystic Fibrosis Receiving Enteral Feeding

subjects drops below 30 before the thirtieth enrolled and active subject completes Study Visit 4 on Day 60 with the intention of finishing the study out to Day 90.

Every effort should be made to collect information regarding UADEs from subjects who drop out or are removed or excluded from the study. Data collected up to the point of withdrawal will be used in the analysis of the appropriate time point but will not be carried forward.

### 4.6 Allowed Concomitant Medications

Subjects should continue all prescribed medications and supportive therapies. Concomitant medications taken for current medical history and birth control are all allowed. Prescription and over-the-counter medications for the treatment of AE/UADEs are permitted.

All supportive therapies and concomitant medications taken by the subject will be recorded in the source documents and entered on the electronic case report form (eCRF). Any dosage changes to concomitant medications required during the study must be recorded in the eCRF.

#### 4.7 Prohibited Medications

There are currently no known interactions to other medications with Relizorb. Treatments with any investigational drug, biologic or medical device are prohibited during the study.

Subjects may use oral PERT with meals and snacks during the day but are prohibited from using PERT or any other medication intended to hydrolyze fat if associated with administration of enteral tube feeding.

# 4.8 Safety Monitoring

### 4.8.1 Study Safety Procedures

Safety data will be monitored on a continual basis throughout the study and clinical changes evaluated. Safety monitoring will include safety follow-up contacts, monitoring AE/UADE, subject withdrawals and safety data. The site monitor will advise the Chief Medical Officer of the frequency and severity of UADEs. The Alcresta Chief Medical Officer will evaluate all UADEs within 24 hours of notification.

Title: Absorption and Safety with Sustained Use of Relizorb™ Evaluation (Assure) Study in Patients With Cystic Fibrosis Receiving Enteral Feeding

# 4.9 Study Procedures

Table 1 lists the timing of assessments and study procedures. If a subject misses a scheduled study visit within the ±4 day window, the visit should be rescheduled as soon as possible.

### 4.9.1 Informed Consent

Each patient must provide written informed consent, as well as assent, when applicable, before any study-related procedure is conducted.

### 4.9.2 Inclusion and Exclusion Criteria

The inclusion and exclusion criteria will be reviewed to determine patient eligibility.

# 4.9.3 Demographics

Subject demographics will document age, gender, and ethnicity.

# 4.9.4 Medical History

On Day -14, a relevant medical history dating back at least 1 year will be obtained. The medical history will emphasize CF disease characteristics, prior therapy, surgery, allergies and assess the patient for any disqualifying medical conditions as specified in the exclusion criteria.

# 4.9.5 Physical Examination

Complete physical examinations are required for all patients entering the study. A qualified member of the study staff (e.g., physician, physician's assistant) will perform a complete physical examination.

### 4.9.6 Height, Weight, and BMI

Height, weight and BMI will be assessed at the time points outlined in Table 1. In addition, study staff will review the medical record and record up to 4 body weights at 3 month intervals recorded over the previous12 months.

# 4.9.7 Vital Signs

Title: Absorption and Safety with Sustained Use of Relizorb™ Evaluation (Assure) Study in Patients With Cystic Fibrosis Receiving Enteral Feeding

After a minimum resting period of 15 minutes, vital signs (heart rate, respiratory rate and sitting blood pressure) will be measured. Oral or tympanic temperature will also be collected.

# 4.9.8 Clinical Laboratory Tests

Blood sample collections will be obtained at the time points outlined in Table 1. Subjects will be in a seated or supine position during blood sample collection.

The clinical laboratory tests to be performed are listed in Table 2 (Clinical Laboratory Tests) below. Handling and shipment of clinical laboratory samples will be analyzed by a central laboratory and be outlined in the laboratory manual.

# 4.9.9 Pregnancy Test

A serum  $\beta$ -hCG pregnancy test will be performed only for females of childbearing potential. Negative results must be available four days prior to the first Relizorb usage on Day 0. If a female subject becomes pregnant while participating in the study, the site is responsible for notifying the Alcresta Chief Medical Officer as soon as possible.

# 4.9.10 Enteral Tube Feeding

During the treatment period (Days 0 to 90), subjects will receive enteral feedings using the same enteral formula, Impact Peptide 1.5. The volume of enteral tube feeding should be 500 to 1000 mL; subjects who routinely receive more or less volume may be enrolled only if approved by the Alcresta Chief Medical Officer. The enteral formula should be delivered using a compatible pump that has a no flow/low flow alarm at a flow rate set between 24 and 120 mL.

Title: Absorption and Safety with Sustained Use of Relizorb™ Evaluation (Assure) Study in Patients With Cystic Fibrosis Receiving Enteral Feeding

**Table 2: Clinical Laboratory Tests** 

Clinical Chemistry	Hematology	Lipids	Urinalysis
Albumin	Complete blood count	Total cholesterol	Bilirubin
Alkaline phosphatase	and white blood cell differential	Triglycerides	Ketones
ALT	unerennar	HDL	Leukocyte esterase
AST		LDL	рН
Bicarbonate			Protein
BUN			Specific gravity
Calcium			Urinary creatinine
Chloride			Urinary uric acid
Cholesterol			
Creatine phosphokinase			
Creatinine			
Glucose			
Lactate dehydrogenase			
Magnesium			
Phosphorus			
Potassium			
Prealbumin			
Sodium			
Total and direct bilirubin			
Total protein			
Uric acid			
A1C levels			
Transferrin			

# 4.9.11 Gastrointestinal Symptom Diary

Detailed verbal instructions on how to record entries in the gastrointestinal symptom diary should be conducted by study staff on Day -14 and again as a subsequent reminder on Days 0, 30, and 60. The gastrointestinal symptom diary will also include a brief instruction. Entries need to occur on a daily basis for 7 consecutive days. The completed symptom diary will be entered into the eCRF and regarded as a source document. Diary data will be used for the primary safety study endpoint to determine the frequency and severity of gastrointestinal symptoms.

Title: Absorption and Safety with Sustained Use of Relizorb™ Evaluation (Assure) Study in Patients With Cystic Fibrosis Receiving Enteral Feeding

# 4.9.12 Plasma and Tissue Fatty Acid Samples

Blood samples will be collected on Day -14 and Day 0 as baseline measures of fatty acid levels. The other fatty acid blood samples will be obtained at the time points specified in Table 1.

# 4.9.13 Fat Soluble Vitamin Samples

Blood samples will be collected on Day -14 and Day 0 to measure baseline fat-soluble vitamin (A, D, and E) levels. The other fat-soluble vitamin blood samples will be obtained at the time points specified in Table 1.

### 4.9.14 Serum Protein Samples

Blood samples will be collected on Day -14 and Day 0 as baseline measures of serum protein (total protein, prealbumin, albumin, transferrin) levels. The other serum protein blood samples will be obtained at the time points specified in Table 1.

# 4.10 Removal of Subjects from the Study

During the course of this study, subjects will be withdrawn and their participation terminated if any of the following occurs:

- Any UADE severe enough in nature to warrant discontinuation in the study
- · Withdrawal of consent
- The site PI, in consultation with the Alcresta Chief Medical Officer, believes the subject should be removed from the study for safety reasons
- Subject is non-compliant with study requirements.

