3.3 Subject Replacement

Approximately 30 to 40 subjects were to be enrolled in the study. Protocol compliant subjects from Protocol 0000497 were eligible for this study, unless clinical changes had occurred in which the patient no longer met the initial eligibility criteria.

Any subject who withdrew from the study before Study Visit 4 on Day 60 was to be replaced by an eligible subject unless enrollment was closed.

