6.2 Handling of Missing Data

Available subject data will be used in the statistical analysis. For the MMRM analysis, subjects who lack all post-baseline measures, the baseline efficacy outcome will be imputed for all post-baseline responses (i.e., no change from baseline).

To handle missing or partial AE and medication dates, the following rules will be applied.

For partial start dates:

- 1. If the year is unknown, then do not impute the date but assign a missing value
- 2. If the month is unknown, then:
 - a. If the year matches the year of the first RELiZORB administration date, then impute the month and day of the first RELiZORB administration date.
 - b. Otherwise, assign "January."
- 3. If the day is unknown, then:

a. If the month and year match the month and year of the first RELiZORB administration date, then impute the day of the first RELiZORB administration date.

b. Otherwise, assign "01."

For partial end dates:

- 1. If the year is unknown, then do not impute the date but assign a missing value.
- 2. If the month is unknown, then assign "December."
- 3. If the day is unknown, then assign the last day of the month.

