8.1 Primary Efficacy Endpoint

Fatty acid erythrocyte tissue composition of the total of DHA plus EPA is the primary efficacy endpoint and is measured at visits 1 through 5 on days -14, 0, 30, 60, and 90, respectively. The primary efficacy endpoint (actual values) will be analyzed by a mixed model repeated measures (MMRM) model to test for LS Mean differences relative to baseline (as defined in Section 6.3) among the post-baseline visits. For this analysis, study visit 2 (day 0), 3 (day 30), 4 (day 60), 5 (day 90) is a categorical effect and subject is a random effect. The primary study population compares baseline to Day 90 in the ITT population. For subjects who lack visit 2, the value at visit 1 will be used.

An unstructured within-subject covariance matrix will be used. If the model does not converge, auto-correlated, and compound symmetry will be explored and the model resulting in the lowest Akaike information criterion value will be presented. LS Means, standard errors (SE), and 95% confidence intervals will be reported by visit. Contrasts in LS Means at each visit against baseline will also be reported with SE and 95% confidence intervals with p-values for differences from zero. A sensitivity analysis of the primary efficacy endpoint will be conducted in the PP population.

Summary statistics for actual values at each visit and changes from baseline will be presented.

The primary endpoint analysis will be repeated by age subgroups and by CFRD subgroups separately.

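### The Day 90 ITT estimate treats subjects who leave after a Day 30 or Day 60 sample as if they had continued on the device, and no planned analysis tests whether this overstates the effect in all exposed subjects

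*Protocol*

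**What the plan says.** - **Leaving the study.** Protocol 4.10 states that "subjects will be withdrawn and their participation terminated if any of the following occurs". The list covers serious device effects, withdrawn consent, safety removal and "Subject is non-compliant with study requirements". Non-compliance is given no threshold.
- **After leaving.** Protocol 4.5 asks sites only for information on unanticipated device effects. The schedule of events (Table 1) has five visits and no withdrawal or off-device fatty acid sample. Protocol 4.5, 7.1 and 7.5 keep the values already collected at their own time points and do not carry them forward.
- **Replacement.** Before Day 60: "Any subject who withdraws from the study before Study Visit 4 on Day 60 must be replaced by an eligible patient". Between Day 60 and Day 90 replacement is optional ("Any subject who withdraws from the study before Study Visit 5 on Day 90 may be replaced by an eligible patient", subject to conditions). SAP 3.3 limits it to losses before Day 60, where the subject "was to be replaced by an eligible subject unless enrollment was closed".
- **Analysis set.** SAP section 5 defines ITT as everyone who used the device at least once.
- **Missing values.** SAP 6.2 uses available data, with one efficacy imputation rule: for "subjects who lack all post-baseline measures, the baseline efficacy outcome will be imputed for all post-baseline responses".
- **Primary analysis.** SAP 8.1: "The primary study population compares baseline to Day 90 in the ITT population". The model is an MMRM with visit as a categorical effect and an unstructured covariance. The only sensitivity analysis named is the per-protocol set.

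**The concern.** Two subjects who stop the device in the same week can be scored in opposite ways. One who leaves just before the Day 30 sample is set to zero change at Day 90. One who leaves just after it has no Day 90 value, and the likelihood supplies one implicitly from the visit pattern of those who stayed. The SAP does not explain the difference.

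Missing at random is doubtful for the second subject. If the device raises erythrocyte DHA+EPA, stopping it should plausibly let the level fall, and no sample is taken that could show this. The study has one arm, so no control group shares and cancels the error. A reader who sees ITT on the primary table will take it as the effect in everyone exposed, when for these subjects it is an on-device prediction.

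**Working it through.** **1. The plan's own figure.** SAP 3.2 gives 80% power for 30 evaluable subjects at effect size 0.53. A two-sided one-sample t-test on the within-subject change at 0.05 gives 0.801. The 0.53 matches 0.8/1.5 = 0.533. The figure reproduces and is not in dispute. The 0.8 and 1.5 are for plasma DHA, whereas the primary endpoint is erythrocyte DHA+EPA, so sizes below are illustrative.

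**2. Inputs.**
- From the documents: Day 90 on-device effect 0.80; SD 1.5, used here for the change.
- Inferred from enrollment targets, not stated as dropout: 35 enrolled to give 30 is 5/35 = 14.3%; 40 to give 30 is 10/40 = 25%.
- Assumed: on-device effects 0.5, 0.7 and 0.8 at Days 30, 60 and 90; exchangeable within-subject correlation ρ of 0.5 or 0.8; late leavers give the Day 30 sample only; a is the share of the Day 30 effect they show (0 to 1); r is the share of the Day 90 effect they keep off device (0 for full return to baseline).

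**3. Effect in all exposed subjects.** With p the share who left, T = 0.80(1 − p) + 0.80·r·p. At r = 0:
- p = 5/35: T = 0.80 × 30/35 = 0.686
- p = 10/40: T = 0.80 × 30/40 = 0.600

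**4. What the planned MMRM estimates.** If all leavers go after Day 30, their Day 90 value is in effect predicted from Days 0 and 30, each with slope ρ/(1 + ρ): 0.333 at ρ = 0.5 and 0.444 at ρ = 0.8. So

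E = 0.80 − p × 0.5 × (1 − a) × ρ/(1 + ρ).

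- 5/35, a = 1: E = 0.800, gap 0.114.
- 5/35, a = 0: E = 0.80 − 0.143 × 0.5 × 0.333 = 0.776 (gap 0.090), or with slope 0.444, 0.768 (gap 0.083).
- 10/40, a = 1: E = 0.800, gap 0.200.
- 10/40, a = 0: E = 0.758 (gap 0.158) or 0.744 (gap 0.144).

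If all leave before Day 30, the zero-change rule applies: E = 0.80 × 30/35 = 0.686, gap 0. For 2 early and 3 late of 35 with a = 1, the late leavers are predicted from 30 stayers and 2 subjects fixed at zero: E = 0.80 × 30/32 = 0.750, gap 0.064.

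**5. Simulation of the same rule** (maximum likelihood, unstructured covariance, zero change for subjects with no post-baseline value):

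| Leavers | MMRM | All exposed | Gap |
|---|---|---|---|
| 5/35, all before Day 30 | 0.69 | 0.686 | 0 |
| 2/35 early, 3/35 later | 0.73–0.76 | 0.686 | 0.05–0.08 |
| 5/35, all after Day 30 | 0.78–0.80 | 0.686 | 0.09–0.11 |
| 10/40, all after Day 30 | 0.73–0.80 | 0.600 | 0.13–0.20 |

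Simulation and formula agree to within about 0.01, which is simulation error. For scale, the standard error is about 1.5/√30 = 0.27. If late leavers keep half the effect (r = 0.5, a = 1), the gap halves: 0.143 × 0.40 = 0.057 and 0.25 × 0.40 = 0.10.

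**6. Does the per-protocol analysis test this?** Its definition requires use through at least Day 30, so it drops the early leavers, who carry the zero-change scores. In the mixed case with a = 1, removing those 2 moves the estimate from 0.750 up to 0.80, whether the 3 late leavers stay in (handled the same way) or are excluded for a major deviation. It moves away from the all-exposed effect of 0.686.

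**The case against.** The strongest reply is that the objective is improved absorption with sustained use, so an on-device Day 90 estimate is legitimate and no bias exists against that target. This stands as far as it goes. The gap exists only relative to the effect in all exposed subjects, and the SAP does not say which effect it is after.

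Stronger readings are tempting, and the documents do not support them:

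- *The ITT result describes compliers.* Non-compliance has no threshold, SAP 9.7 summarizes adherence as a percentage without a cut-off, and SAP 7.2 has a deviation category for product non-compliance. Some poor adherers may therefore remain to Day 90. Early leavers also enter at zero change.
- *Replacement removes the non-compliers.* It adds subjects and deletes none. Anyone exposed once stays in ITT with the values observed.
- *Every departure reflects stopping or misusing the device.* Withdrawn consent and safety removal are also listed.
- *The effect is overstated, by a known amount.* That needs departures after Day 30 and off-device values below the model's prediction. The documents give neither. The same enrollment targets allow no loss at all (30 enrolled, 30 evaluable), and Protocol 1.0 and 4.1 count a subject as evaluable from Day 60.

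The planned outputs do show how many left and why (SAP 7.1), adherence by interval (SAP 9.7), and values for subjects excluded from the per-protocol set (SAP 12.2). These would alert a careful reader, but none estimates Day 90 under a less favourable assumption.

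**Conclusion.** The point holds as a possible, untested upward shift in the primary estimate relative to the effect in all exposed subjects. Its source is the combination of ended participation, no sampling afterwards, and a zero-change rule that stops applying once a single post-baseline value exists. Under a 0.80 on-device effect and full return to baseline, the gap runs from 0 to about 0.20 points, depending mainly on how many leave after Day 30. At its largest that is under one standard error (0.20/0.27 = 0.74). It shrinks in proportion if leavers keep part of the gain, and in this set-up it vanishes if the device has no effect. It therefore bears on the size of the claimed benefit more than on a false positive. The dropout rates, correlation, visit profile and off-device course are all assumptions. A change should be made because the check is cheap and the primary result has no control arm.

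**What to change.** 1. **SAP 6.2 and 8.1.** State that the MMRM estimates an on-device Day 90 effect. Add a sensitivity analysis in which every exposed subject who left and lacks a Day 90 value has a Day 90 change centred on zero, by multiple imputation around the subject's own baseline so that the standard error is honest. Report it beside the MMRM.
2. **Protocol 4.10.** Where consent and safety allow, ask subjects who stop the device to attend the remaining scheduled fatty acid draws, or to give one sample at withdrawal recorded with its actual day. Use these values in that ITT sensitivity analysis. The criteria for removing subjects stay as they are.

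The cost is one extra table, a few blood draws that were already scheduled, and possibly a smaller and noisier estimate. SAP 3.3 describes enrollment in the past tense, so the protocol change may come too late. The SAP change needs no new data and can be made before database lock. If few subjects leave after Day 30, the two results will nearly coincide and the primary claim is the stronger for it.
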